## **Study Protocol**

### **Introduction**

Nearly 18% of United States adults meet criteria for alcohol dependence sometime in their lifetime, with only 24% of those individuals ever receiving any treatment for their disorder (Hasin et al., 2007). The pervasiveness of alcohol dependence indicates a need for continued development of high-impact treatments that are both effective and easily disseminated to a broad population. Recent evidence indicates that Episodic Future Thinking (EFT), the ability to self-project and pre-experience a future event, can help individuals to make changes to habitual behaviors, such as alcohol drinking (Snider et al., 2016). Here, we will evaluate the efficacy of EFT to help individuals reduce alcohol consumption. We anticipate that EFT will result in a reduction in alcohol consumption over a 2-week experimental period when compared to the control group.

### **Participants**

Up to 200 alcohol-dependent adults will enroll in this study. Participants must

- (1) provide written informed consent,
- (2) be 18-65 years old,
- (3) meet DSM-V criteria for moderate or severe alcohol use disorder, and
- (4) express a desire to quit or cut down on their drinking.

Individuals who are pregnant or lactating (through urine screen at time of consent), meet DSM-V criteria for any other moderate or severe substance use disorders (excluding caffeine, nicotine, and marijuana), score 23 or greater on the Alcohol Withdrawal Symptom Checklist (a score indicating that medication would be likely required to manage alcohol detoxification, see Pittman et al., 2007), use prescribed or over-the-counter medicines containing alcohol, participated in any previous studies that included EFT and conducted at the Addiction Recovery Research Center in the last 3 months, or have immediate plans to move out of the area will be excluded from participation. Participants may be compensated based on time and travel.

## **Recruitment**

This project will use recruitment strategies and procedures that are successful in the recruitment and retention of the targeted samples at the Addiction Recovery Research Center. Specifically, participants will be recruited from the Roanoke and Blacksburg, VA communities using IRB-approved study advertisements via posted flyers, and the Internet (e.g., Craigslist, Facebook, etc). Advertisements will include descriptions of the studies and contact information.

To the extent possible, we will attempt to minimize obstacles to participation. For example, travel barriers will be addressed by providing transportation or parking costs to participants, and scheduling barriers will be minimized by offering a flexible assessment schedule. All methods and measurement will be conducted using standard operating procedures, and all staff (including recruitment staff) will be provided with cultural

sensitivity training. We have a history of successful recruitment of alcohol-dependent adults into research programs. All participants will enroll on a voluntary basis and sign an IRB-approved consent form prior to study participation.

## **Consenting Process**

Potential participants will be given adequate time in a quiet room to read the written consent form. VTCRI research staff will review each element of the written consent form with the potential participant. The potential participant will be given the opportunity to ask questions and will have as much time as they need to decide whether they would like to participate in the study. Staff will reiterate that the potential participant can choose to decline participation in the study at that time or at any time thereafter without consequence. The potential participant and person obtaining consent will sign the consent form after the potential participant verbally states that s/he understands the conditions of the study, has no more questions, and chooses to participate.

## **Procedures**

Study design. After the initial consent and assessment sessions, participants will be asked to provide daily self-report assessments of previous-day drinking over cell phone (see below) for 7 days with no other study intervention taking place. The purpose for this baseline period is to quantify baseline drinking patterns and ensure that the participant reliably responds to and conveys study information via cell phone. At the end

of this baseline period, participants who indicated adequate patterns of drinking and successfully reported their level of drinking as requested on baseline days will be invited to continue in the study. Participants will return to the laboratory to be provided with a SOBERLINK breathalyzer and be given instruction in its use.

Participants will be counterbalanced to either the active or control group based on alcohol use (e.g., average drinks per day). Both groups will be exposed to the same treatment events. The intervention period will last for 14 consecutive days, with three breathalyzer screens per day. During this 14-day period as they did during the baseline period, participants will self-report their previous-day alcohol use daily with a text message and/or phone call. Assessment sessions will be conducted prior to the intervention, immediately following the intervention, and at a 1-month follow-up.

Participants will be provided with a prepaid cell phone (if necessary) at the beginning of the study and a SOBERLINK breathalyzer at the beginning of the 14-day period, and receive a \$50 study completion bonus at the end of the study provided these devices are returned.

Cellular phone communication. All participants will either be allowed to use their own personal cell phone for study communications or receive a prepaid cell phone with service through a nationwide cell phone service provider that specializes in providing powerful usage controls with their cell phones, allowing us to restrict phone communication to a study phone and 911 service. If a participant chooses to use his or her personal cell phone for study communications and pays for text messages and/or phone calls on a per unit basis, we may reimburse the participant for the cost of those

messages and calls made for this study. We have used study-provided cell phones to facilitate study communication previously (Koffarnus et al., 2011).

SOBERLINK breathalyzer monitoring. The SOBERLINK breathalyzer ([www.soberlink.net](http://www.soberlink.net)) contains a number of technological advances that make it ideally suited for remote breath samplings of alcohol use. To complete scheduled breathalyzer assessments, participants will simply blow into the device for 4 seconds. During the assessment, a picture is automatically taken of the user, which can be compared to a reference picture taken at study intake. The SOBERLINK device will automatically upload the breathalyzer results, the participant's location, and the picture of the user to a centralized, secure website where the data will be available to research staff. An on-screen display will notify participants of their blood alcohol content as indicated by expired Breath Alcohol Content (BrAC) as a percentage, and confirm submission if successful or instruct participants to redo the assessment if not successful for any reason (e.g., insufficient air flow to measure BrAC). Research staff will monitor these results and verify that the picture matches a reference picture for that participant.

All participants will be asked to complete breathalyzer screens 3 times per day for 14 days. A period of 14 days was chosen to determine if this procedure could result in alcoholic drink reduction using the EFT intervention. At the study onset, participants will be asked to designate the time at which each of the three breathalyzer screens will be scheduled each day. Participants will be asked to choose an assessment time shortly after they usually awaken, shortly before they go to bed at night, and one throughout the

day. They will be allowed to choose any times for the screens, excluding the hours between midnight and 5 am, provided that they are each separated by at least 6 hours. This will ensure that the first and last screens each day will be at least 12 hours apart and the screens will be distributed throughout the day, maximizing the likelihood of detecting alcohol use without placing an unreasonable burden on the participant. Throughout the intervention phase of the experiment, participants will be required to submit three daily breathalyzer assessments at the predetermined times. They will be reminded via text message when a sample is to be collected, and samples will be accepted up to 15 minutes before the scheduled time and 30-60 minutes after the scheduled time, giving the participant 45-75 minutes total to submit the sample. Both groups will receive a \$1 payment for each breathalyzer result submitted within the allowed submission period, regardless of the result of that test. This payment is to encourage participants to complete screens, even if they had consumed alcohol that day. Breathalyzer schedules will be similarly arranged for both groups.

**Intervention.** Participants will be assigned to either the active Episodic Future Thinking (EFT) condition or the control Episodic Recent Thinking (ERT) condition. EFT participants will generate positive future events they are looking forward to and that could happen at different future time points (e.g., in 2 weeks, 1 month, 6 months, 1 year) and participants in the ERT condition will list positive recent events (events that have already happened) that they enjoyed that occurred at different past time points (e.g., 12 hours ago, 24 hours ago, 1 week ago). Participants will be instructed to use and think about their episodic cues as they make decisions. All participants will be provided

with a copy of their episodic cues to take home with them and will receive periodic text messages from research staff to remind them of their cues. Research staff will be available throughout business hours and periodically during evening and weekend hours to deliver text messages and payments. Participants who choose breathalyzer assessment times late at night (e.g., after 8pm) will receive the corresponding payments the following day. Participants will have immediate access to these payments as soon as they are deposited by research staff (see below).

Daily alcohol use self-reports. Each day, participants will be asked to report how many alcoholic drinks they consumed the previous day (from the time they awoke to the time they fell asleep). We will ask them about the previous day alcohol use instead of the current day to best capture all drinks consumed each day without inconsistent response times complicating the measurement. Participants will be allowed to report this information at any time throughout the day, but will be encouraged through prompts to do so in the morning to increase the likelihood of accurate recall of previous day use. Participants will be allowed to report this information via text message or phone call. Participants will receive a reminder to report their previous-day drinking with text messages, followed by a phone call if they haven't contacted us by early evening. For completing this daily self-report, participants will receive \$1 in compensation.

Assessment sessions. Assessment sessions will be completed before the 14-day intervention period, immediately after the 14-day intervention period, and at a 1-month follow-up. Participants will complete a battery of questionnaires and tasks grouped into

three general categories: measures of substance use (including a urine test for drug and alcohol metabolites and a breath sample to test for recent alcohol use), clinically relevant measures including treatment acceptability, and measures of alcohol value and sensitivity.

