RMET15-955 Episodic Thinking (ET) as a Candidate Technique to Reduce
Alcohol Consumption

Statistical Analysis Plan

10/26/2017

Statistical Analysis Plan

Descriptive statistics, chi-square, and t-test will be used to compare means and frequencies of sample characteristics among the two groups. Paired t-tests will be carried out to compare alcohol consumption, rates of discounting, alcohol valuation, PANAS measures, and craving scores before and after the intervention within groups. Discounting of delayed money will be assessed using an adjusting-delay task (Koffarnus and Bickel 2014) and an adjusting-amount task (see Du, Green, and Myerson 2002). Discount rate in both tasks will be calculated using the following hyperbolic equation, (Mazur 1987)

$$V = \frac{A}{1 + kD}$$

In this formula, V refers to the discounted value of a delayed reward; A represents the amount of the delayed reward; D equals the delay of the award; and k represents the delay-discounting rate (Mazur 1987). A higher k value means steeper discounting curve and reflects greater impulsivity, while lower k value means shallower discounting curve with less impulsivity. To provide an estimate of k , we will fit the hyperbolic equation to participants' indifference points (given in discounted monetary value), and use its natural log transformation in analyses. All the statistical analyses will be conducted using Prism 7 at a significance level of 0.05.

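### Allocation is described only as counterbalancing on drinking; with no random element, ratio or concealment stated, the text permits foreseeable or hand-chosen assignment

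*Protocol*

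**What the plan says.** The protocol's Procedures section (Study design) gives one sentence on method: "Participants will be counterbalanced to either the active or control group based on alcohol use (e.g., average drinks per day". Under Intervention it adds only "Participants will be assigned to either the active Episodic Future Thinking (EFT) condition or the control Episodic Recent Thinking (ERT) condition". Neither sentence names a random element, a sequence, a ratio, strata, a minimisation rule or concealment, and the SAP adds nothing on how the groups are formed.

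The surrounding text matters too:

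- Drinking is reported daily over a 7-day baseline whose stated purpose includes quantifying it.
- At the end of baseline, "participants who indicated adequate patterns of drinking and successfully reported their level of drinking as requested on baseline days will be invited to continue". No threshold is given for an adequate pattern.
- After assignment, participants "will receive periodic text messages from research staff to remind them of their cues".
- Entrants must "express a desire to quit or cut down on their drinking" (Participants).
- The hypothesis is comparative: "We anticipate that EFT will result in a reduction in alcohol consumption over a 2-week experimental period when compared to the control group" (Introduction).
- The SAP plans this on comparability: "Descriptive statistics, chi-square, and t-test will be used to compare means and frequencies of sample characteristics among the two groups". Its outcome tests are paired, covering measures up to "craving scores before and after the intervention within groups".

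**The concern.** A claim that EFT reduces drinking relative to control depends on the arms differing only by chance before treatment. Counterbalancing on drinks per day protects drinks per day. It does nothing for other traits that predict drinking over the next two weeks. Strength of intent is an obvious one, since the entry criterion admits people who want to quit and people who want to cut down. Random, concealed assignment protects such traits in expectation.

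The text allows two weaker procedures. In the first, a deterministic sequential rule gives the next person whichever arm best evens out drinking. Staff who can see the data could then foresee the arm, influence who continues and, by bringing someone forward or holding them back, influence which arm that person gets. In the second, staff balance the groups by hand and choose the arm directly. The undefined part of the continuation decision gives either route somewhere to act. The SAP's baseline comparisons can reveal imbalance only in traits that are measured, and would not correct it.

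**Working it through.** **1. The text.** There is no stated figure to reproduce. The two allocation statements give a balancing variable and nothing else. That variable appears to be known before assignment: the baseline period comes first and exists to quantify drinking. The protocol does not say which measurement is balanced, so this is an inference, though a natural one. It is also an inference that some staff know past assignments, from the fact that research staff send the cue reminders. Nothing says those staff are separate from whoever decides on continuation.

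**2. How much steering would produce a given imbalance (illustration).** Let the trait have SD 1.

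- *At the continuation decision, arm fully foreseen, candidates perfectly ranked on the trait.* Suppose the lowest share p is turned away when EFT is next and the highest share p when control is next. The imbalance is 2φ(z_p)/(1−p). For p = 0.0203: 2 × 0.0490/0.9797 = 0.10 SD. For p = 0.0732: 2 × 0.1390/0.9268 = 0.30 SD. This leaves out the timing route. If the arm is guessed correctly with probability g, multiply by (2g−1).
- *Hand-chosen arm for a share q of participants, by the sign of the trait.* The imbalance is 2√(2/π) × q = 1.596q. For q = 0.063 it is 0.10 SD; for q = 0.188 it is 0.30 SD.

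**3. Effect on a between-group test (illustration).** Assume an imbalance of 0.1 to 0.3 SD and a trait-outcome correlation of 0.3 to 0.5. The bias is 0.1 × 0.3 = 0.03 SD to 0.3 × 0.5 = 0.15 SD. With n per arm, SE = √(2/n), and the error rate is P(|Z + bias/SE| > 1.96). The protocol gives only a ceiling of 200 in total, so two sizes are shown.

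| n per arm | SE | Shift (in SE) | Error rate |
|---|---|---|---|
| 50 | 0.200 | 0.15 to 0.75 | 5.3% to 11.7% |
| 100 | 0.141 | 0.21 to 1.06 | 5.5% to 18.5% |

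With no steering the rate stays at 5%.

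**4. Foreseeability and balance of the alternatives.** These figures come from simulation with 100 participants and baseline drinks either normal or lognormal (log-SD 0.6). The sequential rule minimises the absolute count imbalance plus the absolute standardised drinks imbalance. Blocks are of size 4, 6 or 8 within strata split at the median. The last column is the SD, over repeated trials, of the between-arm difference in mean baseline drinks, in SD units of drinks.

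| Method | Next arm guessed: values and past assignments visible | Next arm guessed: less visible | SD of drinks difference |
|---|---|---|---|
| Deterministic rule | about 100% | about 74% (arm totals only) | 0.02 to 0.04 |
| Minimisation, 0.8 coin | 80% | 66% to 67% (arm totals only) | 0.04 to 0.06 |
| Stratified blocks | 68% | 50% (past assignments hidden) | 0.12 to 0.15 |
| Simple randomisation | 50% | 50% | 0.20 to 0.21 |

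A random element lowers foreseeability, but visibility of past assignments matters as well. With full visibility the factor (2g−1) is still 0.60 for the 0.8 coin and 0.36 for blocks.

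**The case against.** The strongest reply is that this is missing detail rather than a poor method. Counterbalancing may be shorthand for stratified randomisation or for minimisation with a random component. The protocol's front matter was not available and may carry a design label. The Recruitment section says that methods follow standard operating procedures, and allocation detail may sit there. All of this stands as a limit on the claim. A reader might infer that the trial was non-randomised, or that staff steered participants; the documents support neither. But a design label would not supply a method or concealment, and a general reference to operating procedures under Recruitment does not state one. The operative sentence, followed literally, needs no random step.

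A second reply is that the figures are not evidence. That is right: the imbalance, the correlation, the perfect ranking and the arm sizes are all assumed, and the between-group test is one the SAP does not plan. The missing test is a separate matter and does not remove the need for comparable arms.

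Third, nothing establishes that motivation goes unmeasured, because the assessment battery includes clinically relevant measures that are not itemised. This also stands. The point needs only that balancing on drinking does not protect other traits, measured or not.

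Finally, central release of assignments does not by itself remove the problem, since it hides upcoming assignments but not past ones. That is correct and shapes the fix.

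**Conclusion.** The point holds as a gap in the stated method: balance on drinking is specified, but nothing is stated that would keep assignment unpredictable or out of staff hands. It is a cheap improvement that should be made, held with medium confidence because a random element may already be in use.

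The size of any bias cannot be derived from the documents. The error rates above hold only if steering occurs at the assumed strength, and should not be quoted as the trial's actual error. Nor should near-certain prediction of the next arm be taken as a property of this trial: it requires a deterministic rule together with sight of baseline values and past assignments.

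**What to change.** Replace the allocation sentence under Study design with concealed, computer-generated assignment at a stated ratio (for example 1:1) that keeps balance on baseline average drinks per day. Either of two methods will do:

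- minimisation on drinks per day with a random element, which stays closest to the sponsor's balancing aim and needs no cut-point; or
- permuted blocks of varying size, stratified at a cut-point fixed in advance.

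Fix the continuation criterion in advance (the threshold is the sponsor's to choose), and record each continuation decision before the assignment is released centrally. As far as staffing allows, whoever decides on continuation should not see past assignments or running totals. If concealed random assignment is already used, state it.

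The cost is one protocol paragraph, a list or minimisation routine, and some separation of tasks from the staff who send cue reminders. The statistical price is somewhat looser balance on drinks per day at 50 per arm: small for minimisation and larger for stratified blocks, as the last column of the second table shows.

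### The arms are counterbalanced on baseline drinking, but no listed method adjusts an EFT-ERT comparison for it; an unadjusted t-test would report too large a standard error

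*Protocol*

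**What the plan says.** The Protocol (Procedures, Study design) starts with seven days of daily drinking reports. Of this week it says: "The purpose for this baseline period is to quantify baseline drinking patterns". Allocation follows: "Participants will be counterbalanced to either the active or control group based on alcohol use (e.g., average drinks per day". The balancing algorithm, the number of strata and the allocation ratio are not described.

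The Introduction states a between-arm hypothesis: "We anticipate that EFT will result in a reduction in alcohol consumption over a 2-week experimental period when compared to the control group".

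For comparisons between groups, the SAP says: "Descriptive statistics, chi-square, and t-test will be used to compare means and frequencies of sample characteristics among the two groups". For outcomes it says: "Paired t-tests will be carried out to compare alcohol consumption", together with discounting, alcohol valuation, PANAS and craving, and it limits the scope to "craving scores before and after the intervention within groups". It does not mention counterbalancing and names no covariate, stratum or model with a group term. The only model fitted is the hyperbolic curve that yields each participant's k. On software and level: "All the statistical analyses will be conducted using Prism 7 at a significance level of 0.05".

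On size, the Protocol (Participants) says only: "Up to 200 alcohol-dependent adults will enroll in this study". Neither document gives a power calculation, an effect size or a standard deviation.

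**The concern.** Balancing the arms on a variable that predicts the outcome makes the estimated difference between arms less variable than it would be under simple randomization. A test that ignores the balancing variable does not register this: it still counts the spread in baseline drinking as error. The reported standard error then exceeds the true one, the nominal 5% test rejects less than 5% of the time under the null, the confidence interval is too wide, and a real EFT effect is easier to miss.

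The SAP does not specify the EFT-ERT outcome comparison that the hypothesis calls for. Someone adding it later would most naturally use a t-test, the only method for comparing means between groups that the SAP now lists. That repair would carry this error, so adjustment should be written in at the same time.

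**Working it through.** The plan gives no power or precision figure to reproduce, so the check is of direction and size.

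**Inputs from the documents:** balancing on alcohol use; a seven-day baseline; significance level 0.05; at most 200 participants.

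**Assumptions, not in the documents:** 1:1 allocation; close balance on baseline mean drinks, with assignment otherwise at random; a two-sided test; the same SD (σ) at baseline and during the intervention; baseline-outcome correlation r from 0.3 to 0.8. Let n be the number per arm.

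**Step 1, post-score t-test.** It reports SE = σ√(2/n). With the arms matched on baseline, the true SE is σ√(2/n)·√(1−r²). Reported/true = 1/√(1−r²).

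**Step 2, change-score t-test.** It reports SE = σ√(2/n)·√(2−2r). The arms' baseline means are nearly equal, so the difference in change is nearly the difference in post scores, and the true SE is as in step 1. Reported/true = √(2−2r)/√(1−r²) = √(2/(1+r)).

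**Step 3, actual type I error** = 2[1 − Φ(1.96 × ratio)].

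| r | Post-score ratio | Type I error | Change-score ratio | Type I error |
|---|---|---|---|---|
| 0.3 | 1/√0.91 = 1.05 | 4.0% | √(2/1.3) = 1.24 | 1.5% |
| 0.5 | 1/√0.75 = 1.15 | 2.4% | √(2/1.5) = 1.15 | 2.4% |
| 0.7 | 1/√0.51 = 1.40 | 0.6% | √(2/1.7) = 1.08 | 3.4% |
| 0.8 | 1/√0.36 = 1.67 | 0.1% | √(2/1.8) = 1.05 | 3.9% |

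These ratios do not depend on n. At r = 0 the post-score ratio is 1.00.

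**Step 4, simulation** (5,000 runs, 100 per arm, arms formed from ranked pairs; r = 0.3 / 0.5 / 0.7; SEs in SD units).
- Post-score test: reported SE 0.141 against an empirical 0.136 / 0.124 / 0.100; null rejection 4.0% / 2.2% / 0.5%.
- Change-score test: null rejection 1.6% / 2.2% / 3.2%.
- Regression on group and baseline: model SE 0.135 / 0.122 / 0.101 against an empirical 0.136 / 0.123 / 0.099; null rejection 5.2% / 5.0% / 4.6%.
- With simple randomization, the post-score test rejects about 5% of the time at each r. The distortion therefore comes from the balancing.

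**Step 5, coarser balancing.** In a simulation that balanced only on a median split of baseline drinking, the post-score SE was about 3%, 9-10% and 20-23% too large at r = 0.3, 0.5 and 0.7. Type I error was about 4%, 3% and 1.5%.

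**Step 6, power** for an assumed true difference of 0.4 SD = Φ(0.4/true SE − 1.96 × ratio), with ratio 1 for the adjusted analysis.
- r = 0.7, 50 per arm: true SE = √(2/50)·√0.51 = 0.143 and 0.4/0.143 = 2.80. Post Φ(2.80−2.74) = 52%; change Φ(2.80−2.13) = 75%; adjusted Φ(2.80−1.96) = 80%.
- r = 0.7, 100 per arm: 0.4/0.101 = 3.96. Post 89%, change 97%, adjusted 98%.
- r = 0.5, 100 per arm: 0.4/0.1225 = 3.27. Post 84%, change 84%, adjusted 90%.
- r = 0.3, 100 per arm: 0.4/0.135 = 2.96. Post 82%, change Φ(2.96−2.43) = 70%, adjusted 84%.

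**The case against.** The strongest objection is that the SAP lists no test with this fault. Its between-group tests cover sample characteristics, and its outcome tests are paired and within group. A paired test contains no contrast between arms, so this mechanism does not widen its standard error. On this view the real gap is the absent EFT-ERT comparison, and the choice of covariate is a detail of filling it. This stands in part. The missing comparison is the larger gap, and the present point concerns how it should be filled.

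A reader might infer more than the documents support:
- *That the SAP plans an unadjusted EFT-ERT outcome test.* It plans no such test, so the consequence is conditional.
- *That baseline drinking is left out of the analysis altogether.* A pre-intervention value enters the paired test of alcohol consumption. It does not enter as an adjustment between arms.
- *That the precision gained by counterbalancing is lost.* The point estimate keeps it; the reported error fails to show it.

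The size is also open to challenge. The correlation is assumed, the algorithm is unknown, and the balancing variable is itself given only as an example. Since the SAP already works with before-and-after values, a change score may be the natural extension. At r = 0.7 and 50 per arm it has 75% power against 80% with adjustment, a modest gap. That also stands, but it depends on r: at r = 0.5 and 100 per arm the gap is 84% against 90%, and at r = 0.3 it is 70% against 84%. Among the three analyses checked, only the adjusted one held its nominal level at each r simulated.

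**Conclusion.** The point holds in conditional form. The design balances on baseline drinking, the hypothesis is between arms, and no listed method adjusts an EFT-ERT comparison for the balancing variable. An unadjusted comparison would be conservative, by the amounts in the table if balance is close and by less if it is coarse. For outcomes weakly related to drinking, possibly PANAS, the effect of balancing on a post-score test could be negligible.

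The figures rest on an assumed correlation, 1:1 allocation, equal SDs and a two-sided test. The error does not bias the estimate or inflate false positives, so it does not threaten the validity of a positive result. It should still be corrected: the documents state no power margin that could absorb the loss, and the correction uses data the trial already collects.

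**What to change.** State in the SAP that the EFT-ERT difference in intervention-period mean drinks per day is estimated by linear regression (ANCOVA) on group and baseline-week mean drinks per day, the counterbalancing variable, with a 95% confidence interval. Describe how counterbalancing was done and confirm which drinking measure it used.

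If balancing used a few strata, include the stratum as well. Do not add individual pair terms: 100 participants in 50 pairs would need 49 degrees of freedom for them.

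For ln k, alcohol valuation, PANAS and craving, adjust for the outcome's own pre-intervention value. Adding baseline drinks there is optional, as no calculation here supports requiring it.

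The cost is a change of SAP wording and one degree of freedom for baseline drinks, plus one fewer than the number of strata if strata are included. It needs no new data and no new participants. The SAP names Prism 7 for every analysis, so the sponsor should confirm that it fits this model and name other software if it does not.
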